7.3.8 Post-Operative Cochlear Response Telemetry Recording

Post-insertion measures will be obtained using a frequency sweep (with recording from electrode 22 for signals with frequency 250, 500, 1000, and 2000 Hz delivered at a maximum comfortable listening level) and an electrode sweep (with recording using a 500 Hz acoustic signal presented at a maximum comfortable listening level and recording on electrodes 22, 20, 18, 16, 14, 12, 10, 8, 6, 4 and 2). The signal level (typically comprising a 12 ms duration stimulus and 50 ms inter-stimulus interval) will be controlled to ensure comfortable loudness presentation.

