23 APPENDIX A: INSTRUCTIONS FOR MASKING

- a) Pure tone threshold is established in the test ear
- b) Masking noise is introduced to the non-test ear at the initial masking level (10 dB above the established threshold in the non-test ear). Pure tone threshold is then re-established.
- c) Level of the masking tone or noise is increased subsequently by 5 dB. If there is a response to the tone in the presence of the noise, the level of the noise is increased by 5 dB. If there is no response to the tone in the presence of the noise, the level of the tone is increased by 5 dB steps until a response is obtained.
- d) A plateau has been reached when the level of the noise can be increased over a range of 15 to 20 dB without shifting the threshold of the tone. This corresponds to a response to the tone at the same HL when the masker is increased in three to four consecutive levels.
- e) Masked pure tone threshold corresponds to the HL of the tone at which a masking plateau has been established.

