The CM response traces will be examined for any unusual patterns and whether such patterns appear to be associated with any factors (e.g. electrode type). If visual inspection suggests interesting associations in characterizing the CM response, regression analyses will be computed to further understand the predictive influence of the factors on the CM morphology and time-course.

4. *Investigation of the relationship of CM thresholds to postoperative HTLs in the implanted ear.*

This hypothesis will be tested using a repeated measures linear regression to examine the association between CM threshold (independent variable) and behavioural threshold (dependent variable) at FUV2. Thresholds are measured at several frequencies (e.g. 250Hz, 500Hz, 1 kHz, 2 kHz, 4 kHz) and this creates potential correlation within subjects, thus

necessitating repeated measures approach. The thresholds will be expressed in dB nHL. A test of the slope of the CM threshold term against a null hypothesis value of 1 will be performed; a value significantly greater than 1 would indicate behaviour thresholds are higher than the corresponding CM threshold. Frequency will also be examined to understand if there is an effect on the association of CM and behavioural threshold. If the assumption of normality fails based on a Shapiro-Wilk test of normality at the 0.05 level, the data will be arcsine transformed to minimise departure from normality. Descriptive statistics for the CM and behavioural thresholds, the mean (standard deviation) or median (inter-quartile range) as appropriate will be reported by frequency.

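### Exploratory analysis 4 tests a regression slope against 1 to judge whether behavioural thresholds exceed CM thresholds; error in the CM threshold pulls that slope below 1, and a slope does not measure level

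*SAP*

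**What the plan says.** SAP 3.2.4 item 4 plans a "repeated measures linear regression to examine the association between CM threshold (independent variable) and behavioural threshold (dependent variable) at FUV2". The key inferential step is: "A test of the slope of the CM threshold term against a null hypothesis value of 1 will be performed". The SAP gives the reading in advance: "a value significantly greater than 1 would indicate behaviour thresholds are higher than the corresponding CM threshold".

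On the data, it says "Thresholds are measured at several frequencies (e.g. 250Hz, 500Hz, 1 kHz, 2 kHz, 4 kHz", and the repeated-measures model is justified only by the within-subject correlation that this creates. On scale: "The thresholds will be expressed in dB nHL". If normality fails, "the data will be arcsine transformed to minimise departure from normality".

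Protocol 7.3.8 describes the post-operative frequency sweep as "recording from electrode 22 for signals with frequency 250, 500, 1000, and 2000 Hz delivered at a maximum comfortable listening level". That is a single level and omits 4 kHz, so the protocol does not show how a CM threshold, or its precision, is obtained. Protocol 7.2 places post-operative CRT at either FUV1 or FUV2, so the number of subjects with CM data at FUV2 is not fixed.

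For this test neither document states an alpha, a sidedness or a sample size. Neither mentions error in the CM threshold, replicate CM thresholds, a reliability estimate, errors-in-variables regression or limits of agreement.

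**The concern.** A null value of 1, with a slope above 1 read as one threshold exceeding the other, makes this a question of agreement between two measures. Two things then go wrong.

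First, the regression treats the measured CM threshold as exact. Random error in the predictor shrinks the slope toward zero. When the null is zero, that costs power but leaves the test correctly centred. When the null is 1, the test is no longer centred on agreement. Handling within-subject correlation repairs the standard error, not this shift.

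Second, a slope describes how fast one threshold rises with the other, not which is higher. The planned reading does not follow from the planned statistic even with error-free CM thresholds.

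At stake is a statement about whether CM thresholds track behavioural thresholds. Protocol section 4 says the findings will likely inform commercial intra- and post-operative monitoring technology.

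**Working it through.** **Plan's own figure.** Item 4 has no sample size, power or precision to reproduce. The only calculated figure is the primary sample size of 36 per group (15 dB difference, SD 25 dB, one-sided 0.05, power 0.80). It reproduces: exact t power is 0.809 at 36 and 0.7996 at 35. It matters here only as a bound. With 86 subjects and 5% lacking a CM response, 86 × 0.95 = 81.7, so at most about 82 subjects contribute.

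**Inputs.**
- From the SAP: behavioural threshold is the response, CM threshold the predictor, null slope 1.
- From Protocol 7.3.8: 4 frequencies.
- Assumed, because the documents give none: SD of true thresholds 15 to 25 dB; CM-threshold error SD 0 to 10 dB; error independent with mean zero; 20, 40 or 82 subjects; behavioural error SD 5 dB. The last is only suggested by the 5 dB test step in Protocol Appendix A ("the level of the tone is increased by 5 dB steps until a response is obtained"). Behavioural error adds residual noise but does not bias the slope.

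**Attenuation.** Expected slope = true slope × λ, with λ = var(true) / [var(true) + var(error)]. With true slope 1:

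| True SD (dB) | Error 2.5 dB | Error 5 dB | Error 10 dB |
|---|---|---|---|
| 15 | 225/231.25 = 0.97 | 225/250 = 0.90 | 225/325 = 0.69 |
| 20 | 400/406.25 = 0.98 | 400/425 = 0.94 | 400/500 = 0.80 |
| 25 | 625/631.25 = 0.99 | 625/650 = 0.96 | 625/725 = 0.86 |

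A true slope up to 1/λ is expected to appear as 1 or less. For true SD 15 or 20 dB with 5 or 10 dB of error, 1/λ runs from 1.06 to 1.44.

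**Effect on a two-sided 5% test.** Random-intercept regression was simulated with 400 runs per setting and true-threshold SDs of 15 between and 10 within subjects, or 18 and 15. Ranges are over these SDs and the three sample sizes.

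| CM error | True slope 1: mean slope | Rejected as below 1 | True slope 1.2: mean slope | Detected as above 1 |
|---|---|---|---|---|
| 0 dB | 1.00 | 2–4% | – | – |
| 3 dB | 0.97–0.98 | 10–32% | 1.16–1.18 | 96–100% |
| 5 dB | 0.92–0.96 | 28–96% | 1.10–1.15 | 55–100% |
| 10 dB | 0.69–0.83 | 93–100% | 0.82–0.99 | 0–4% |

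The random-intercept model can attenuate more than λ, because within-subject information is diluted more. With SDs 15 and 10 and 10 dB error, λ = 325/425 = 0.76, but the simulated slope at 82 subjects is 0.70.

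A separate simulation used ordinary regression with subject-clustered errors (40 subjects, true SD 20 dB, 2,000 runs). With a true slope of 1.1, it found a slope above 1 in 99.6%, 94.4%, 22.1% and 0.1% of runs at 0, 2.5, 5 and 7.5 dB error.

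**Effect on an upper-tailed test.** In that second simulation with true slope 1, the upper tail of the two-sided test rejected in 3.2% of runs with no error, 0.6% at 2.5 dB and none from 5 dB upward. The upper-tailed test becomes conservative.

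**Slope versus level, without any error.** If behavioural threshold = CM threshold + 10 dB throughout, the slope is exactly 1 although behavioural thresholds are always higher. If behavioural threshold = 80 + 1.2 × (CM threshold − 80), then CM thresholds of 70, 80 and 90 give 68, 80 and 92. The slope is 1.2, but the mean difference is (−2 + 0 + 2)/3 = 0.

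**Alternatives.** Zero-mean CM error does not bias the mean behavioural-minus-CM difference. Its test rejected in 3.7 to 6.0% of runs throughout the second simulation. That is a test of a different null, the one the SAP's stated reading needs; it does not show that the slope test is repaired. A Deming slope with the correct error-variance ratio (40 or 82 subjects, CM error 5 or 10 dB) averaged 0.996 to 1.003 under agreement, with total rejection 4.5 to 8%. It detected a true slope of 1.2 in 92 to 100% of runs.

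**The case against.** A reader might infer that the analysis will reject perfect agreement and hide a true slope above 1. The documents do not support that. Both outcomes depend on CM-threshold error, the spread of true thresholds and the number of subjects at FUV2, none of which they give for this analysis. With 3 dB of error, agreement is usually not rejected and a slope of 1.2 is nearly always found; both harms are severe together only at about 10 dB.

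Sidedness also matters. Item 4 states none, but the only outcome it interprets is a slope above 1, and the SAP's other tests with a stated alpha are one-sided. An upper-tailed test cannot reject because the slope is too low, so the false-rejection figures above would not apply. This stands in full.

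Item 4 is also framed as association, with CM threshold as predictor. For predicting behavioural threshold from a measured CM threshold, the uncorrected slope is the right quantity. That stands for a descriptive slope, but not for a test against 1 read as one threshold exceeding the other.

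The SAP already plans descriptive statistics for both thresholds by frequency, so a gross level difference would be visible, though without a paired estimate or interval. Finally, Deming regression brings its own unknown, the error-variance ratio, so it is not a clean replacement.

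**Conclusion.** The planned slope test cannot soundly support the conclusion attached to it. Under independent, zero-mean CM error, the direction of the bias is certain: toward slopes below 1, with lost power for slopes above 1. The amount cannot be stated without CM-threshold reliability. Over the assumed ranges it goes from negligible (about 1 to 3% attenuation at 2.5 dB error) to dominant (14 to 31% at 10 dB). Whether false rejection or only conservatism follows depends on the unstated sidedness. The mismatch between slope and level needs none of these assumptions.

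Priority is low: this is one exploratory analysis, separate from the primary and secondary endpoints.

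**What to change.** In SAP 3.2.4 item 4:

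- For the claim that behavioural thresholds are higher, replace the slope-versus-1 test with a repeated-measures model of the within-subject difference, behavioural minus CM threshold in dB nHL, with frequency as a factor. Report the mean difference with 95% CI, and limits of agreement that allow for repeated measurements per subject. State the alpha and sidedness of any test.
- Keep the regression slope with its interval as a description of association or prediction, and remove the sentence that reads a slope above 1 as higher behavioural thresholds.
- If proportionality is of interest, add a Deming slope over a stated range of error-variance ratios, with intervals from a bootstrap that resamples subjects, as a sensitivity analysis.
- Remove the arcsine fallback. It is undefined for values outside −1 to 1, so it cannot be applied to thresholds in dB as they stand, and a transformed difference would no longer read in dB.

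The cost is a few lines of SAP wording and no new data. The optional Deming slope needs an assumed error ratio. The mean difference is protected against random CM error but would still carry any systematic error in how the CM threshold is determined, so the SAP should say how that threshold is obtained.

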**Investigation Schedule**

Procedure	POV1 Pre-operative	D0 Surgery	FUV1 4-6 Weeks Post-Surgery (+/- 1 week)	FUV2 3-Month Post-Activation (+/- 2 weeks)
Medical and Hearing History	X			
Otoscopy (Check for Wax Occlusion)	X	X	X	X
Cochlear Response Telemetry (CRT)		X	X (either FUV1 or FUV2)	
Audiometry & Tympanometry	X		X	X
Surgical Questionnaire		X		
Impedance Measures (Standard, 4-point, Voltogram)		X	X (either FUV1 or FUV2)	
Optional (where obtained at sites as part of routine clinical management): Imaging (MRI Pre-Operative; X-Ray or Cone Beam CT Post-Operative)	X		X	

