Furthermore, to inform Cochlear's future technology and product development of intra-operative monitoring tools that utilize ECoG measures, it is of interest to examine the influence of pre-operative acoustic hearing status on the characteristics of the CM response during intra-cochlear insertion of the electrode array. Understanding further the factors that influence the characteristics of the CM response (e.g. onset and latency) might enable reference markers to be incorporated within future software monitoring tools as to expected behavior of the CM response for cochlear implant recipients with varying characteristics. Additionally, it may be possible to provide reference data regarding expected responses for different electrode types. The CRT system provides the capability to interleave measures of electrode impedance with the ECoG recordings, which is expected to provide an ability to track the progressive entry of electrodes into the cochlea during insertion (through observed reduction in impedance when electrodes are in contact with perilymph). The combined use of such impedance measures and ECoG recordings will be used to characterize the CM response as a function of the number of electrode contacts inside the cochlea. Earlier CM onset is expected with better high frequency acoustic hearing, since the electrode array initially advances through the basal region of the cochlea passing the outer hair cells that are responsive to the high frequencies. Although maximum hair cell response to the 500 Hz acoustic tone occurs in the apical region the cochlea, hair cell populations in the basal region will also respond to the travelling wave. Latency change will be measured between two CM onset points and is predicted to increase as the advancing electrode passes surviving inner and outer hair cells populations. If there is no measurable high frequency hearing, it is hypothesized that CM amplitude will increase without an increase in latency as the electrode advances towards the apex.

Postoperative CRT sweeps will be conducted immediately following the wound closure (baseline) and at either 4-6 weeks post-surgery or at 3 months post-implantation. This will allow changes over time in different components of the ECoG to be characterized. The relationship between hearing threshold levels (HTLs) in the implanted ear and ECoG responses at FUV1 or FUV2 (e.g. CM and acoustic neurophonic response (ANN) thresholds) will also be examined.

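### SAP exploratory item 4 takes a slope above 1 to mean higher behavioural thresholds, which a slope alone cannot show, and its arcsine fallback cannot be run on dB values

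*SAP*

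**What the plan says.** SAP 3.2.4, item 4, plans a repeated-measures linear regression for the association "between CM threshold (independent variable) and behavioural threshold (dependent variable) at FUV2". The slope is tested against a null value of 1, and the SAP adds that "a value significantly greater than 1 would indicate behaviour thresholds are higher than the corresponding CM threshold". On scale it says: "The thresholds will be expressed in dB nHL". If a Shapiro-Wilk test rejects normality at the 0.05 level, "the data will be arcsine transformed to minimise departure from normality". Frequency is to be examined as a factor. "Descriptive statistics for the CM and behavioural thresholds" are to be reported by frequency, as means or medians with their spread.

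Item 4 does not mention the intercept, a fit through the origin, or a test of the paired difference. It gives no alpha, sidedness or sample size for the slope test, and no step that turns dB values into proportions.

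**The concern.** Whether one threshold is higher than the other is a question of level. A slope answers a different question: how many dB the behavioural threshold rises for each dB of CM threshold. Adding the same constant to every behavioural threshold moves the intercept and leaves the slope and its test exactly as they were. The planned test therefore carries no information about level unless something is known about the intercept.

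As written, one significant result would be read the same way whether behavioural thresholds were higher throughout, lower throughout, or crossed over within the range. A clear constant offset would pass unnoticed by the test.

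The fallback has a different fault. Arcsine is a transformation for proportions and has no value for ordinary audiometric thresholds. If the data were first rescaled to make it computable, a null slope of 1 would no longer carry its dB meaning.

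**Working it through.** The plan states no figure for this analysis, so there is none to reproduce.

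**Step 1: algebra (no assumed data).** With behavioural = a + b·CM, the difference is D = a + (b − 1)·CM. For b > 1, D is positive only where CM > −a/(b − 1). At b = 1.2, for CM from 50 to 100 dB:

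| a | D at CM 50 | D at CM 100 | Crossover −a/0.2 | Truth |
|---|---|---|---|---|
| −5 | −5 + 10 = +5 | −5 + 20 = +15 | 25 dB | higher throughout |
| −15 | −15 + 10 = −5 | −15 + 20 = +5 | 75 dB | crosses |
| −30 | −30 + 10 = −20 | −30 + 20 = −10 | 150 dB | lower throughout |

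The reverse also occurs. With a = +30 and b = 0.8, D = 30 − 0.2·CM is +22 dB at CM 40 and +10 dB at CM 100, so behavioural thresholds are higher although the slope is below 1. With a = +15 and b = 1, D is +15 dB everywhere and the slope equals its null value. For positive thresholds and b > 1, the SAP's reading is safe only if a is zero or positive.

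**Step 2: how often the test would mislead (illustrative).** Assumed, because the SAP gives no values: 35 subjects × 4 frequencies, CM uniform on 50–100 dB, subject SD 6 dB, residual SD 6 dB, a frequency term, cluster-robust standard errors on 34 df, two-sided 5%, 2,000 runs per cell. Percentage of runs with slope significantly above 1, by SD of CM measurement error:

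| True line | 0 dB | 4 dB | 6 dB | 8 dB |
|---|---|---|---|---|
| a = −5, b = 1.2 (higher) | 96.9 | 54.8 | 5.9 | 0.05 |
| a = −15, b = 1.2 (crosses) | 96.3 | 54.4 | 5.9 | 0.1 |
| a = −30, b = 1.2 (lower) | 96.1 | 55.5 | 5.5 | 0.05 |
| a = +15, b = 1 (15 dB higher) | 2.6 | 0.05 | 0 | 0 |

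Within each column the first three rows agree up to simulation error: the test cannot tell these situations apart.

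The fall across columns is attenuation. The variance of CM is 50²/12 = 208.3, so the expected slope is b × 208.3/(208.3 + error SD²). For b = 1.2 this gives 1.20, 1.11, 1.02 and 0.92 (simulated means 1.20, 1.12, 1.02, 0.92). With no true difference at all (a = 0, b = 1), the slope was significantly below 1 in 2.0%, 27.3%, 75.3% and 97.8% of runs.

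**Step 3: the paired difference under the same settings.** The mean of behavioural minus CM, tested against 0, was significant with the correct sign in 100% of runs for a = +15, b = 1; for a = −30, b = 1.2; and for a = −5, b = 1.2. With no difference it was significant in 4.4% to 5.2%. For the crossing line (a = −15, b = 1.2) the true mean difference is 0, and it was significant in 4.6% to 5.2%.

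**Step 4: the arcsine.** arcsin(y) needs −1 ≤ y ≤ 1, and arcsin(√y) needs 0 ≤ y ≤ 1. Neither exists at 20, 80 or 126 dB. The protocol admits thresholds up to 80 dB HL at 500 Hz (7.5.1), and SAP 3.2.2 codes non-measurable post-operative thresholds as 126 dB HL. If values are first divided by an assumed maximum M, a constant +15 dB offset over CM 50–100, whose dB slope is exactly 1, gives:

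| M | slope after arcsin√(y/M) | slope after arcsin(y/M) |
|---|---|---|
| 120 | 1.16 | 1.23 |
| 126 | 1.11 | 1.18 |
| 150 | 1.02 | 1.09 |

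The slope now depends on M, so 1 is no longer a meaningful null value.

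**The case against.** The strongest reply is that this is one loosely worded sentence and one underspecified fallback in an exploratory item, which the protocol (7.1.4) says only may be performed. Testing a slope against 1 is a legitimate check of proportionality, and item 4's stated aim is the relationship between the two thresholds. The by-frequency descriptives would show an offset, and would also contradict a reading of higher if behavioural thresholds were 10 to 20 dB lower throughout. All of this stands and limits the harm. It does not make the SAP's sentence correct.

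The 96% figures depend on error-free CM and a slope of 1.2. At an error SD of 6 dB the rate for a = −30 falls to 5.5%. With a = −20 and b = 1.1 (truly 10 to 15 dB lower), it was about 50%, 6%, 0.4% and 0% at the four error levels. The simulation also draws CM independently across frequencies within a subject. The percentages are therefore illustration, and the case rests on the algebra. The results for slopes below 1 are a caution about attenuation and not an SAP error, since the SAP attaches no meaning to such slopes.

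On the fallback, SAP 3.2.2 does contain an audiometer ceiling of 126 dB HL. But that is a coding rule for the primary analysis, and nothing makes it a rescaling constant for item 4. Rescaling would make the arcsine computable, but the null value of 1 would still lose its meaning.

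**Conclusion.** The concern holds, at minor severity. The interpretive sentence is wrong as written for any regression with a free intercept; this follows from the model alone and needs no assumed figures. The arcsine step cannot be carried out on thresholds as the SAP expresses them, and it matters only if the normality test rejects. How often a misleading result would occur depends on unknown CM measurement error, slope and intercept: in the illustration, from about 96% with error-free CM to almost never at an error SD of 8 dB. No primary or secondary endpoint depends on this analysis.

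**What to change.** In SAP 3.2.4, item 4:

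- Delete the sentence that infers level from the slope. The slope test can stay as a check of proportionality.
- Test the mean paired difference (behavioural minus CM) against 0 in the planned repeated-measures model, keeping the frequency term.
- Report slope and intercept together with intervals, and the predicted difference at low, middle and high CM. This is needed because the mean difference misses a difference that changes sign (step 3). Note that CM error attenuates the slope.
- Replace the arcsine step with a method valid in dB, such as a robust or bootstrap interval, and state that normality is judged on residuals.

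Two clarifications can be made in the same edit; they add no weight to the finding. First, item 4 places the analysis at FUV2, but the protocol's schedule allows post-operative CRT at either follow-up visit, and Protocol section 4 refers to "hearing threshold levels (HTLs) in the implanted ear and ECoG responses at FUV1 or FUV2". State whether FUV2 applies to both measures, and pair CM and behavioural thresholds from the same visit. Second, the SAP's example frequencies ("e.g. 250Hz, 500Hz, 1 kHz, 2 kHz, 4 kHz") include 4 kHz, whereas the post-operative frequency sweep in Protocol 7.3.8 stops at 2000 Hz. Confirm whether a CM threshold is obtained at 4 kHz.

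The cost is SAP wording only, with the same data and the same model family.
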